6.3.1 RSA procedure

The RSA set-up consist of two synchronized roentgen tubes positioned approximately 1.5 meter above two roentgen cassettes (35 X 43 cm) at a 20° angle to the vertical. Both roentgen tubes simultaneously expose the roentgen film (Figure 2). A calibration box is used to calibrate the experimental set-up.

The RSA X-ray which is taken one or two days after surgery (before loading) is used as baseline. Since the tantalum beads are fixed in the bone around the implants, the position of the implant relative to the bone can be calculated. Taking these bone markers as reference points, the spatial translations and rotations of the component during follow-up can be calculated.(22, 29) The bone markers need to be well fixated in the bone. Bone markers are defined unstable when they move more than 0.3 mm with respect to the other bone markers. Unstable markers will be excluded from analysis.(30) When there are not enough markers visible in the baseline RSA X-ray and this does not improve by placing the patient in another position, the patient will be excluded from the study (secondary exclusion criterium).

[figure not shown]

Figure 2: A uniplanar RSA arrangement. Two X-ray tubes are focused on the joint under examination. A calibration cage is placed underneath the X-ray table. It holds two X-ray films positioned next to each other.(22)

6.4 Withdrawal of individual subjects

Subjects can leave the study at any time for any reason if they wish to do so, without any consequences. They will be asked for the reason for withdrawal, but do not have to answer if they do not want to. Furthermore, the investigator can decide to withdraw a subject from the study for urgent medical or other reasons.

When a patient withdraws from the study, all data collected prior to the moment of withdrawing will be used for study analysis, unless the patient also withdraws consent for use of this data.

6.4.1 Specific criteria for withdrawal (if applicable)

6.5 Replacement of individual subjects after withdrawal

Subjects for which not enough markers are visible on the first RSA-radiograph will be excluded from the study. These patients will be replaced, to ensure that a minimum of 25 patients per group remain.

Subjects who withdraw from the study for other reasons than the amount of visible markers will not be replaced, as long as a minimum of 20 patients per group remains. Otherwise, additional subjects will be recruited.

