3.3 RSA procedures

Roentgen Stereophotogrammetric Analysis (RSA) will be used to determine the micromotion of the components with respect to the bone. For this purpose, one-millimetre-diameter tantalum beads will be inserted in the surrounding bone of the prosthesis during surgery using a special insertion instrument.

The RSA X-ray which is taken one or two days after surgery is used as baseline. When there are not enough markers visible in the baseline RSA X-ray and this does not improve by placing the patient in another position, the patient will be excluded from the study (secondary exclusion criterium).

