6.1.2 Secondary study parameters/endpoints (if applicable)

Physical functioning, quality of life, pain and patient satisfaction will be scored with PROMs, consisting of: numeric rating scale (NRS) for pain in rest and during loading, Hip disability and Osteoarthritis Outcome Score Physical Short form (HOOS-PS), EQ-5D and an anchor question about general daily functioning. All PROMs will be collected prior to surgery, at 6 months, 1 year, 2 years and 5 years after surgery. All implant related (serious) adverse events including reoperations and survival of the THA (cup and stem component) will be collected up to 5 years after surgery.

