6.2 Randomisation, blinding and treatment allocation

After signing informed consent, the patients will be randomized in one of the three study groups by the researcher, using an online randomisation program (CASTOR). Patients will be blinded for group allocation. The principal investigator and the participating surgeons may divert from the randomization scheme based on intraoperative findings. Any deviation from the assigned treatment group will be reported as a deviation from protocol.

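### Patients with too few visible RSA markers leave the whole study after randomisation and surgery, so their later PROM, safety, survival and CT follow-up is lost without need

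*Protocol*

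**What the plan says.** **Order of events.** Section 6.2: "After signing informed consent, the patients will be randomized in one of the three study groups by the researcher". Surgery follows. Section 6.3.1: "The RSA X-ray which is taken one or two days after surgery (before loading) is used as baseline".

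**The rule.** If too few markers show on that image and repositioning does not help, sections 3.3 and 6.3.1 say that "the patient will be excluded from the study (secondary exclusion criterium". Section 6.5 repeats it: "Subjects for which not enough markers are visible on the first RSA-radiograph will be excluded from the study". It then adds: "These patients will be replaced, to ensure that a minimum of 25 patients per group remain". Subjects who leave for other reasons "will not be replaced, as long as a minimum of 20 patients per group remains".

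**Data already collected.** Section 6.4 provides that, for a patient who withdraws, "all data collected prior to the moment of withdrawing will be used for study analysis", unless consent for this is also withdrawn. Section 6.6 likewise uses data up to drop-out.

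**Outcomes other than RSA.** Section 6.1.2: "All implant related (serious) adverse events including reoperations and survival of the THA (cup and stem component) will be collected", for up to 5 years. The same section schedules PROMs before surgery, at 6 months and at 1, 2 and 5 years. Section 6.1.1 schedules CT at discharge and 2 years, and section 6.1.3 uses CT for cement mantle thickness as well.

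**Experience with the cup.** Section 4.3 says that no clinical study of the BiMobile cup has been done before this one.

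**The concern.** A patient without a usable baseline RSA image has no RSA migration value, so leaving that analysis cannot be avoided. The protocol goes further and takes the patient out of the study. At that moment the patient has been randomised and has received the implant, and almost every secondary and safety outcome still lies ahead.

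Two things are at stake.

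- **The safety and survival record of a new cup.** Patients would leave it for an imaging reason that has nothing to do with safety. The protocol plans no DSMB (section 7.5). Its one interim look counts SAEs when 15 patients have reached 6 months (section 8.4), a point that a patient excluded on day 1 or 2 never reaches.
- **The comparison as randomised.** This is an exclusion after randomisation, applied to outcomes that do not call for it. The arms differ in cup size and cement mantle (A against B) and in make (C), and the beads lie in the bone around the cup. Marker visibility might therefore differ by arm. That is a possibility only: the protocol gives no rates, overall or by arm.

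An analysis plan cannot repair this later, because the rule decides which data are collected.

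**Working it through.** **1. The plan's own figure.** Section 2.4 gives 25 per group and 90% power for equivalence, with margin 0.3 mm, SD 0.3 mm and true difference 0. For two one-sided tests in normal form, power = 2Φ(margin / (SD√(2/n)) − z) − 1. With n = 25 the first term is 1/√0.08 = 3.536.

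- At 0.05 per side: 2Φ(3.536 − 1.645) − 1 = 94.1%.
- At 0.025 per side: 2Φ(3.536 − 1.960) − 1 = 88.5%.

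The stated 90% lies between the two. The point does not challenge this figure, and the fix leaves 25 RSA-evaluable patients per group as they are.

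**2. What follow-up needs a usable baseline RSA image.**

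| Outcome | Timing | Depends on the baseline RSA image? |
|---|---|---|
| RSA migration | to 2 years | Yes |
| RSA against CT (paired comparison) | discharge, 2 years | Yes, through the RSA half |
| PROMs | 6 months, 1, 2, 5 years | No |
| Implant-related events, reoperations, survival | to 5 years | No |
| CT migration, CT mantle thickness | discharge, 2 years | Not stated to |

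For an exclusion on day 1 or 2, sections 6.4 and 6.6 keep the preoperative data, the surgical details, very early events and possibly the discharge CT. In a survival analysis such a patient adds one or two days out of five years.

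**3. How many patients.** The protocol gives no failure rate x, so x is an assumption. To retain 75 patients, the number excluded is 75/(1 − x) − 75.

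- x = 5%: 78.9 − 75 = 3.9
- x = 10%: 83.3 − 75 = 8.3
- x = 15%: 88.2 − 75 = 13.2

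Rounding 25/(1 − x) up within each arm gives 27, 28 or 30 randomised per arm, so 6, 9 or 15 excluded in total.

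**4. How many revisions.** Section 5.4 gives a five-year revision rate of 4.0% for the Avantage cup. Applying it to all arms is an assumption, since there is no clinical figure for the BiMobile cup.

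- Among the retained 75: 75 × 0.04 = 3.0, or 1.0 per arm.
- Among the excluded: 3.9, 8.3 or 13.2 × 0.04 = 0.16, 0.33 or 0.53 over all three arms.

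Excluded patients come on top of the 25 retained per arm, because they are replaced. The share of revisions lost therefore equals the failure rate itself, 5% to 15%.

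**The case against.** The case for leaving the text alone has real content.

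- **Nothing already collected is thrown away.** A reader might infer that the rule discards these patients' data. Section 6.5 handles them under withdrawal, and sections 6.4 and 6.6 keep data up to that point. This stands: the loss is of later follow-up.
- **The primary endpoint is not harmed by the rule.** Without a baseline there is no migration value, and the trigger comes before any migration can be seen. This stands. The gain from a change lies in the secondary and safety outcomes.
- **Bias between arms is not shown.** A reader might infer that exclusions will differ by arm. No figure in the protocol supports that. Visibility may also depend on bead placement and patient position, and the protocol provides for quick feedback and retakes (section 6.3) and repositioning (sections 3.3 and 6.3.1). These lower the number affected; they do not change what happens to those who remain.
- **An arm's revision count is not at risk of being halved or erased.** With about 1 revision expected per arm, a reader might fear this. It does not follow, because the retained 25 still expect 1.0 and the excluded patients are extra.
- **Replacements are not said to go into a chosen arm.** A reader might infer that the per-group minimum lets the next allocation be known. Section 6.2 randomises through CASTOR with no exception for replacements, and the minimum can be met by continuing three-arm randomisation. At most the wording is unclear.

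What the objection does not answer is why patients who can still give PROM, safety, survival and CT data should stop giving them.

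**Conclusion.** The point holds as a cheap improvement, not as a flaw that threatens the primary result. Three sections remove randomised and operated patients from the whole study on the ground of an image needed only for RSA, and no section keeps them in follow-up for anything else. At assumed failure rates of 5% to 15%, about 4 to 13 patients are affected. At the Avantage rate of 4.0%, about 0.16 to 0.53 expected revisions would go unrecorded over all arms. Losing a revision is thus possible rather than likely. Both ranges rest on assumptions that the protocol cannot confirm: the failure rate is not given, and the revision rate belongs to the comparator cup. The finding itself, that later follow-up is lost without need in the first clinical trial of the BiMobile cup, rests on the text alone.

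**What to change.** - In sections 3.3, 6.3.1 and 6.5, limit the exclusion to the RSA migration analysis.
- State that these patients stay in follow-up for PROMs, adverse events, reoperations and survival to 5 years, and for the CT scans already planned.
- Report the number of marker failures by arm. This also shows whether visibility differs between cups.
- Keep the target of 25 RSA-evaluable patients per group.
- As a clarification only, state in section 6.5 that replacements enter through the same three-arm CASTOR randomisation.

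**Cost.** Questionnaires and event follow-up for a few more patients; the planned 2-year CT for each of them, at 0.3 mSv (section 4.4), in patients who have no RSA endpoint; and slightly unequal arms.

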2.4 Sample size calculation

Based on current RSA studies and the high degree of sensitivity and accuracy of measurements of migration, relatively small patient groups should show statistical significant outcome.(22) A standardized phantom experiment for the model-based RSA, was performed with an acetabulum cup (Delta-TT cup, LINK) under simulated *in-vivo* conditions (Table 1). In such a phantom experiment, there is no actual movement between the components and the bone, therefore, the observed relative motions represent the

measurement error of these specific components using model-based RSA. These standard deviations are good estimations for the accuracy of the method that can be achieved *invivo*. The relative motions presented in table 1 are smaller than the accepted relative motions presented by Baad-Hansen et al.(23)

Table 1: Relative motions of the Delta-TT cup with respect to the acetabulum bone markers calculated using the elementary geometric shape (EGS) model (n = 10).

	Translations (mm)			Rotations (deg)			
	Trans (x)	Long (y)	Sag (z)	Trans (x)	Long (y)	Sag (z)	
Mean	0.001	0.003	-0.009	-0.069	-0.033	0.033	
St. dev	0.094	0.041	0.074	0.182	0.276	0.396	
Min	-0.145	-0.048	-0.113	-0.410	-0.493	-0.833	
Max	0.170	0.098	0.101	0.137	0.314	0.618	

Sample size calculation based on a t-test was done, assuming normal distribution of migration data and standard deviation of translation of 0.3 mm within the patient collective at two years follow-up.(23) When the sample size in each group is 25, a two group 0.05 t-test will have 90% power to reject the null hypothesis that the two cups are not equivalent (= the difference in means, is 0.3 mm or farther from zero in the same direction) in favour of the alternative hypothesis that the means of the two groups are equivalent, assuming that the expected difference in means is 0 and the common standard deviation is 0.3 mm. This difference of 0.3 mm translation can be considered as a clinically relevant difference.

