8. STATISTICAL ANALYSIS

Descriptive data will be summarized by treatment group. For parameters represented by continuous variables, the summaries will consist of the mean, median, standard deviation, interquartile range, minimum, and maximum values. For categorical variables, the number and percentage in each category will be presented.

Continuous outcome variables and their differences will be analysed with parametrical statistical techniques, unless the normality assumption does not seem reasonable for the data, in which case non-parametric techniques will be considered. A two-sided 0.05 alpha level will be used.

A paired t-test will be used to measure the differences in translations and rotations between RSA and CT.

Actions will be taken to minimize the amount of missing data. If data is missing, this will be handled according to the instructions of the specific measurement instrument, or if not available, imputation techniques will be used to replace the missing data.

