8.1 Primary study parameter(s)

The main study parameter is the early migration (translational and rotational movements) of the BiMobile 2 mm cement acetabular cup and the BiMobile 4 mm cement acetabular

Version number: 3.0, date 20-12-2021 23 of 31

cup after two years. RSA data (discharge, 6 weeks, 6 months, 1 year and 2 years postoperatively) will be analysed using repeated measures ANOVA or mixed models if certain data points are missing. The null hypothesis is that there is no significant difference in mean migration at all time points. The alternative hypothesis is that the mean migration is significantly different at one or more time points.

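### The 90% power in section 2.4 holds at 25 per group but falls to about 86–87% at the 20 per group that section 6.5 permits, and no single primary migration variable is named

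*Protocol*

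**What the plan says.** **Power.** Section 2.4 of the protocol reads: "When the sample size in each group is 25, a two group 0.05 t-test will have 90% power". The target is equivalence. For translation, the null hypothesis is that "the difference in means, is 0.3 mm or farther from zero in the same direction", and the power is computed "assuming that the expected difference in means is 0 and the common standard deviation is 0.3 mm". A second paragraph makes the same statement for rotation, with 0.8 degree as both margin and standard deviation. Neither paragraph adds patients for loss to follow-up.

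**Replacement.** Section 6.5 replaces patients with too few visible markers on the first RSA image, so as to keep 25 per group. Patients who withdraw for other reasons "will not be replaced, as long as a minimum of 20 patients per group remains"; recruitment resumes only below that number.

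**Level and hypothesis.** Section 8 states: "A two-sided 0.05 alpha level will be used". Section 8.1 sets a null hypothesis of no difference in mean migration over the time points, tested by repeated measures ANOVA or, if data points are missing, by mixed models.

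**Primary parameter.** Section 8.1 begins: "The main study parameter is the early migration (translational and rotational movements". It names no axis and no rule for combining axes. Section 6.1.1 has migration measured by both RSA and CT. The Summary names RSA alone for the main endpoint, and section 8.2 puts the CT analysis under secondary parameters.

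**The concern.** The power statement and the replacement rule describe different trials. One assumes 25 per group; the other accepts a finished trial with 20, a loss of 5/25 = 20%. Follow-up to the main endpoint is two years, in men of at least 70 and women of at least 65, so some loss is to be expected. The ethics committee and readers see only the figure for 25.

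The power is also a per-variable figure, while the main parameter is a set of variables. Table 1 lists three translations and three rotations. With no axis singled out, the protocol does not say which result decides the main question, and separate tests at 5% on each axis would raise the chance of a false positive well above 5%.

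**Working it through.** **Inputs.** Section 2.4 gives n = 25 per group, level 0.05 and true difference 0. The margin and SD are both 0.3 mm for translation and both 0.8 degree for rotation, so margin/SD = 1 in both and one calculation serves for both. Section 6.5 gives the floor of 20. Section 8 gives the two-sided 0.05 level.

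**Step 1: standard error in SD units,** √(2/n).
- n = 25: √(2/25) = 0.283, so margin/SE = 1/0.283 = 3.536.
- n = 20: √(2/20) = 0.316, so margin/SE = 1/0.316 = 3.162.

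**Step 2: the protocol's own figure (equivalence, 25 per group).** For two one-sided tests (TOST) at 0.05 per side with true difference 0, the normal approximation to power is 2Φ(margin/SE − 1.645) − 1.
- n = 25: 2Φ(1.891) − 1 = 94.1%; exact t, 93.4%.
- n = 20: 2Φ(1.517) − 1 = 87.1%; exact t, 85.6%.

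The stated 90% is therefore met at 25, with some slack.

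**Step 3: the difference test of section 8.1,** as a two-sided 0.05 comparison at two years with a true difference of one SD. Normal approximation: Φ(margin/SE − 1.960).
- n = 25: Φ(1.576) = 94.2%; exact t, 93.4%.
- n = 20: Φ(1.202) = 88.5%; exact t, 86.9%.

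**Step 4: exact results under each possible reading, one variable.**

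| Test | n = 25 | n = 20 | n per group for 90% |
|---|---|---|---|
| TOST, 0.05 per side | 93.4% | 85.6% | 23 |
| Two-sided 0.05 difference test | 93.4% | 86.9% | 23 |
| TOST, 0.025 per side (not stated in the protocol) | 86.7% | 73.8% | 27 |
| One-sided 0.05 test (at odds with section 8) | 96.7% | 92.8% | 18 |

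In the first two rows the slack at 25 is 25 − 23 = 2 patients per group, while section 6.5 permits a loss of 25 − 20 = 5.

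Those two rows nearly coincide because 0.3 mm serves both as the equivalence margin and as the difference to detect, and the quantile sums at 90% power are close: 1.645 + 1.645 = 3.290 for equivalence, 1.960 + 1.282 = 3.242 for a difference. The hypotheses are still different ones.

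**Step 5: several axes.** If each of k independent axes is tested at 5% with no adjustment, the chance of at least one false positive is 1 − 0.95^k.
- k = 3: 1 − 0.857 = 14.3%.
- k = 6: 1 − 0.735 = 26.5%.

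Positive correlation between axes lowers these figures.

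**The case against.** Four points speak for the protocol.

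- **The power claim is conditional and true.** It is stated for 25 per group and is met there. A reader might infer that the protocol promises a power it does not have, or that the sample size arithmetic is wrong. The documents do not support that: section 2.4 is correct as far as it goes, and it covers a translation and a rotation separately.
- **The shortfall at 20 is small and depends on the test.** Under the two main readings it is 3 to 4 points. A one-sided 0.05 test would keep about 93% at 20. The same-direction wording of section 2.4 leaves room for that reading, but the two-sided level in section 8 speaks against it. In the other direction, a reader might take the two-sided 0.05 level to mean 0.025 per side for equivalence, giving 87% and 74%. The protocol nowhere says so, and these figures are only a sensitivity check.
- **Withdrawn patients are not wholly lost.** Sections 6.4 and 6.6 keep data collected before withdrawal, and section 8.1 allows mixed models, so part of the loss may be recovered. This stands, but section 2.4 powers a two-group t-test and claims no such gain. Moreover, the floor in section 6.5 counts patients, not evaluable two-year RSA images, and section 6.3.1 removes unstable markers from analysis. The number of evaluable cups could be below 20.
- **Axis and multiplicity can be left to a statistical analysis plan.** That is often so, and such a plan may exist. Here, however, the protocol itself defines the main parameter as a set of movements and gives conflicting accounts of whether CT belongs to it. That conflict has to be settled in the protocol.

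A reader might also infer that all six axes must succeed and that power therefore collapses. Section 8.1 contains no such rule. It tests for a difference, so the risk that follows from several axes is a raised false-positive rate.

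**Conclusion.** The point holds in a limited form. Single-variable power is about 93% at 25 per group and about 86–87% at the permitted floor of 20; 90% needs 23. This rests on margin/SD = 1, a true difference of 0 for equivalence or one SD for the difference test, 0.05 per side or two-sided 0.05 respectively, and a complete-case two-group comparison at two years. The last is only an approximation to the planned repeated-measures analysis.

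The main parameter is not reduced to one variable, and the place of CT is stated inconsistently. If six axes were each tested at 5% without adjustment, about 26% false positives would follow under independence.

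A linked weakness is that section 2.4 powers equivalence while section 8.1 tests for a difference. The power figures happen to be close, but the quoted power belongs to a hypothesis other than the one to be tested. None of this makes the trial unsound; it should be corrected because the remedy is a matter of wording.

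**What to change.** 1. In sections 6.1.1 and 8.1, name one RSA migration variable at two years as primary. The choice of axis is the sponsor's, on clinical grounds.
2. Make the other axes and CT secondary, and bring the Summary and sections 6.1.1, 8.1 and 8.2 into line.
3. Restate section 2.4 for that variable, for the hypothesis that section 8.1 tests and with the significance level and sidedness written out. Give power at both 25 per group (about 93%) and the permitted 20 (about 86–87%). These figures assume that margin/SD stays at 1; if the chosen variable has a different SD, recompute them.

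The cost is a few sentences and a slightly less favourable stated power. No extra patients are needed.
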